### 3.5.4. Additional analyses

#### Model Assessment

The results of additional regressions will be reported and will be clearly labeled as such and will be sharply distinguished from the primary prespecified outcome. These analyses serve two purposes: (a) assessment of how sensitive the final analytic result is to the prespecified analytic choices, and (b) facilitation of future meta-analytic or review studies. In particular, results will be reported in both absolute and relative scales. Model adequacy will be checked by examination of residuals or other goodness of fit tests as needed. Inadequate model fit will prompt us to report alternative models. As a supplemental, sensitivity analysis, we will estimate permutation  $P$ -values for each comparison using a randomization test proposed by Simon and Simon, which re-estimates the allocation probabilities within each permutation rather than treating them as fixed [9].

#### Subgroup Analyses

Pre-specified subgroup analyses for mortality constitute secondary outcomes for the trial. They include:

- Region (Dosso, Tahoua, Maradi, Zinder, Tillaberi). Rationale: examine effect heterogeneity by geographic region.
- Child age (1-11m, 12-24m, 24-59m). Rationale: examine effect heterogeneity by age within each treatment regimen
- Child sex. Rationale: consistent with US NIH reporting of sex as a biological variable.
- Community distance to the nearest Centre de Santé Intégré (CSI). Rationale: previous analysis of the MORDOR trial in Dosso, Niger found larger mortality reductions in communities further from CSIs.
- Number of previous community distributions. Rationale: examine whether effects wane with number of treatments.
- Timing of distribution / seasonality. Rationale: examine effect heterogeneity by season, as mortality could vary by season.
- Other Interventions
  - Participation in the MORDOR trials (Dosso region)
  - Seasonal Malaria Chemoprevention (SMC) in the most recent malaria season if it occurred within the three months prior to the current treatment period. Rationale: examine if there is effect heterogeneity depending on co-delivery with SMC. SMC coverage. Rationale: examine if there is effect heterogeneity depending on co-delivery with high coverage SMC.
  - Trachoma distributions of azithromycin: any distribution received by other programs during the AVENIR trial. Rationale: effect could be attenuated among communities that receive additional treatment. Number of distributions received before and during the AVENIR trial. Rationale: examine effect heterogeneity by the quantity of past and concurrent azithromycin treatments outside of the trial.

- Nutritional status as defined by weight, mid-upper arm circumference (MUAC), height interval. Rationale: determine if there is effect heterogeneity by child nutritional status measured by anthropometry.

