4.3. Timeline

The study will take place over a 4-year period beginning Fall 2020 (Table 1).

Implementation will be phased in by region. Study progress is defined in “census rounds” which refer to a single 6-month census data collection and treatment period, and “inter-census intervals”, which refer to the interval between two census rounds, required to assess the primary outcome of mortality in the Mortality Trial. Dosso will be enrolled in the first year and Tahoua in the second year. Parts of Tahoua and Maradi will be added to the Programmatic Trial in the second and third years.

Table 1. Estimated eligible study population and communities with intervention roll out in Stage I and II.

Region	Stage I ¹							Stage II ²		
	Estimated eligible under-5 population ³	Estimated eligible communities	Year 1		Year 2		Year 3	Year 3		Year 4
			Round 1	Round 2 ⁴	Round 3 ⁵	Round 4	Round 5	Round 6	Round 7	Round 8
Dosso	271,273	1,800	X*	X	X	X*	X*	X	X	X
Tahoua (1)	245,944	1,225			X	X*	X	X	X	X
Tahoua (2)	245,944	1,225				X	X	X	X	X
Maradi (1)	342,889	1,000					X	X	X	X
Maradi (2)	342,890	2,000						X	X	X
Zinder	452,241	3,860							X	X
Tillabéri	440,791	3,070								X
Total:	2,341,972	14,180								

X = census and/or treatment; X* = census and/or treatment + resistance collections in a sample of communities

¹Stage I through primary outcome analysis at 2.5 years from the first enrollment.

²Stage II dependent upon primary outcome, resources, and security restrictions.

³As estimated from projections by the Institute for Health Metrics and Evaluation multiplied by fraction of eligible grappes in each region.

⁴Delivery trial will begin at the beginning of round 2 in year 1

⁵Interim analysis at approximately 1.5 years (end of round 3). At this time, intervention will begin in Programmatic Trial Communities.

Table 2. Estimated eligible population by trial and region for Stage I.

Region	Estimated eligible under-5 population ¹	Estimated eligible communities ²	Mortality/Resistance trial communities ^{3,4}	Delivery trial communities	Programmatic communities
Dosso	271,273	1,744	1,584	160	0
Tahoua	491,888	1,916	1,416	0	500
Maradi (1 st half)	342,889	1,000	0	0	1,000
Total	1,106,050	4,660	3,000	160	1,500

¹As estimated from projections by the Institute for Health Metrics and Evaluation multiplied by fraction of eligible grappes in each region.

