4.4.8.4. Measurement of Additional Outcomes

Data on other programs that include the distribution of antibiotics in the study area will be collected. Seasonal Malaria Chemoprevention (SMC) implementation and coverage data will be collected from SMC implementers at the district and community level during the study. Trachoma distributions will be tracked, and prior distributions recorded for each community through communications with PNSO.

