### 3.5.2. Analysis methods

#### Mortality in the mortality/resistance trial

Our parameter of interest for comparisons of mortality between arms is the relative reduction in mortality measured by the incidence rate ratio (IRR). The primary analysis will be a Poisson regression that includes the count of deaths as the outcome and the community-level person-time at risk as an offset, with observations for each community's inter-census interval. The model will include an indicator variable for each active treatment arm. The adaptive allocation will be accounted for using pooled regression, including in the model additional indicator variables for each of three allocations in the trial (the initial, equal allocation plus 2 adaptations). For community  $i$  and randomization  $j$  ( $j = 1, 2, 3$ ), the model will be:

$$\log(Y_{ij}) - \log(T_{ij}) = \alpha + \beta A_{ij} + \sum_{j=2}^3 \gamma_j P_j,$$

where  $Y_{ij}$  is the number of deaths and  $T_{ij}$  is the person-time at risk in that community;  $A_{ij}$  is a treatment indicator that will vary by each comparison (details below), and  $P_j$  is an indicator for the two adaptive random allocations (the first equal allocation is the omitted category). We will

estimate 95% confidence intervals for the IRRs using bootstrap resampling (10,000 replicates) that resamples communities with replacement and re-estimates the IRRs.

For primary outcome 1 that compares mortality among 1-59 month olds, we will include in the analysis children ages 1-59 months in the 1-59 month treatment arm and placebo arm.  $A_{ij}$  will be an indicator of allocation to the 1-59 month treatment arm, and  $\exp(\hat{\beta})$  will estimate the IRR.

For primary outcome 2 that compares mortality among children ages 1-11 months, we will subset the analysis to children ages 1-11 months enrolled in the 1-11 month treatment arm and placebo arm.  $A_{ij}$  will be an indicator of allocation to the 1-11 month treatment arm, and  $\exp(\hat{\beta})$  will estimate the IRR.

Similarly, for primary outcome 3 that compares mortality among children ages 12-59 months, we will subset the analysis to children ages 12-59 month in the 1-11 month treatment arm and 1-59 month treatment arm.  $A_{ij}$  will be an indicator of allocation to the 1-59 month treatment arm, and  $\exp(\hat{\beta})$  will estimate the IRR.

Secondary mortality analyses will be estimated similarly from the model subset to the appropriate age range.

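### The trachoma subgroup in SAP 3.5.4 reads as a whole-trial community flag, so follow-up before the outside distribution would be coded as exposed and the attenuation contrast diluted

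*SAP*

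**What the plan says.** The Subgroup Analyses list in SAP 3.5.4, whose mortality items are secondary outcomes, has two trachoma modifiers. The first is "Trachoma distributions of azithromycin: any distribution received by other programs during the AVENIR trial", with the reason that the "effect could be attenuated among communities that receive additional treatment". The second is "Number of distributions received before and during the AVENIR trial", meant to show heterogeneity by the amount of earlier and simultaneous outside azithromycin. Neither is tied to a date or to an interval.

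The seasonal malaria chemoprevention (SMC) item in the same list is tied to time. It counts a campaign only "if it occurred within the three months prior to the current treatment period".

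SAP 3.5.2 fits the mortality model "with observations for each community's inter-census interval" and examines modifiers through interactions with treatment. It does not say how a modifier that changes during follow-up is coded. On the data side, Protocol 4.4.8.4 says: "Trachoma distributions will be tracked, and prior distributions recorded for each community through communications with PNSO".

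**The concern.** An outside distribution cannot change deaths that came before it. If a Dosso community has a trachoma distribution at month 20, a whole-trial flag still labels its intervals 0–6, 6–12 and 12–18 months as exposed. In those intervals the trial effect should be the same as in communities with no outside azithromycin, so the flagged group becomes a mixture and its rate ratio moves toward the unflagged one.

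The subgroup exists to look for attenuation, and this error runs against finding it. A weak or null interaction could then be read as reassurance that outside azithromycin does not matter. The SMC item shows that the authors anchor an exposure in time where they think of it.

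**Working it through.** The documents give no figure for this subgroup (number of communities affected, dates or expected attenuation), so there is none to reproduce. The background figures do reproduce: 1,400×4 + 975×2 + 975×1 = 8,525 intervals, 3,350/3 ≈ 1,116 communities per arm, and 79.2% power for primary outcome 1 against about 80% stated.

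**Inputs from SAP 3.2.3.** Placebo rate 27 per 1,000 person-years; 10% relative reduction (rate ratio 0.90, treated rate 24.3); the follow-up schedule above.

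**Assumptions.** One outside distribution per flagged community. Before it, the rate ratio is 0.90. After it, the placebo rate falls to 24.3 (rate ratio 1.00, full attenuation), and this lasts to the end of follow-up. Let *f* be the share of flagged follow-up that comes after the distribution.

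**Formulas.** Flagged rate ratio = 24.3 / [*f*×24.3 + (1−*f*)×27] = 0.90 / (1 − 0.1*f*). Share of the log-scale interaction kept = ln(1 − 0.1*f*) / ln(0.90).

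**Neutral timing within follow-up**

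- Uniform over the community's own follow-up: *f* = 0.50.
- Uniform over calendar months 0–24, weighted by community-months (Dosso 1,400×24 = 33,600; Tahoua 975×12 = 11,700, entering at month 12, and 975×6 = 5,850, entering at month 18). The pre-distribution shares are 0.50, 0.25 and 0.125, so the weighted share is (16,800 + 2,925 + 731)/51,150 = 0.40 and *f* = 0.60.
- Equally likely at the start of each interval: *f* = 0.625 with four intervals, 0.75 with two and 1 with one. Weighted, (5,600×0.625 + 1,950×0.75 + 975×1)/8,525 = 0.70.

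| *f* | Flagged rate ratio | Interaction kept |
|---|---|---|
| 1.00 (no dilution) | 1.000 | 100% |
| 0.70 | 0.967 | 69% |
| 0.625 | 0.960 | 61% |
| 0.60 | 0.957 | 59% |
| 0.50 | 0.947 | 49% |
| 0.25 (late) | 0.923 | 24% |
| 0.125 (very late) | 0.911 | 12% |

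**Sensitivity.** With half attenuation (0.95 after the distribution) the shares are almost the same: 49% at *f* = 0.50 and 62% at 0.625. Taking the 14% reduction cited in the Protocol's background (0.86) and mixing rate ratios directly gives 0.5×0.86 + 0.5×1.00 = 0.93, and ln(0.93/0.86)/ln(1/0.86) = 52% kept.

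**Precision.** SAP SD 0.023, 1,116 per arm and an assumed 30% of communities flagged give SE = √[2×0.023²/(1,116×0.3) + 2×0.023²/(1,116×0.7)] = 0.00212. Power to detect full attenuation (difference 0.0027*f*) is about 25% at *f* = 1, 12% at 0.625 and 9% at 0.50.

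**The case against.** **The SAP never says that earlier intervals are coded as exposed.** This is true. The one-row-per-interval structure would allow coding by date, and neighbouring modifiers are naturally interval-level. But the written definition refers to the trial and not to the interval, and nothing tells the analyst to do otherwise. Either the rule misclassifies or one sentence is missing; the text changes in both cases.

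**A reader might infer that the attenuation is largely washed out.** The documents do not support that. Neutral timing keeps about half or more, and 12–25% remains only for late distributions. A more extreme figure, 75% of Dosso follow-up preceding the distribution and 26% of the interaction kept (with 0.86), needs distributions counted anywhere in the whole study ("The study will take place over a 4-year period beginning Fall 2020"). The subgroup outcome is mortality over 2.5 years (SAP 3.5.1), and later rounds are conditional (Protocol Table 1).

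**A reader might infer that the companion count credits future distributions to past intervals.** Its stated rationale covers only earlier and simultaneous treatment, which points the other way. It needs a cut-off date in the wording, no more.

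**One distribution per community is an assumption.** With two, uniformly timed over 24 months, the expected share before the first is one third and 65% is kept.

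**Comparing communities that ever had outside treatment is a legitimate question.** It is, as description, and the rationale does speak of communities. It does not isolate attenuation after an outside dose.

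**Power is low anyway.** It is about 25% even without dilution, on the assumption above. That limits what any result can show, but the point estimate is still biased.

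**Interval coding brings its own confounding.** This stands. Exposed intervals fall later in the trial, and the SAP 3.5.2 model adjusts for allocation group but not for round, so attenuation could be mixed with waning over successive distributions. The fix has to deal with it.

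**Conclusion.** The point holds as a defect in a prespecified secondary subgroup. On its plain reading the trachoma modifier labels pre-distribution follow-up as exposed and biases the contrast toward no difference. If attenuation is real, roughly 50–70% of the log-scale interaction is kept under neutral timing, and less if distributions come late.

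That range rests on one distribution per flagged community within follow-up and an outside dose that acts to the end of follow-up. If its effect wanes sooner, the dilution is greater; the documents give no duration. They also give no number of affected communities, so the practical weight of this subgroup is unknown. No primary mortality or resistance test is touched.

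**What to change.** In SAP 3.5.4:

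1. Define the first modifier per community inter-census interval: exposed if an outside azithromycin distribution occurred during the interval or within a stated lookback before its opening census. The length of the lookback is for the sponsor to choose and justify; the documents give no basis for one.
2. Define the companion count as the cumulative number of outside distributions up to the closing census.
3. State that no distribution dated after an interval is used to classify it.
4. In this subgroup model include census round, as a main effect and by treatment.
5. Keep the community as the resampling and permutation unit, as SAP 3.5.2 already plans, because one community can now contribute to both strata.

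**Cost.** SAP wording and a merge of distribution dates onto intervals. The Protocol says that distributions are tracked with PNSO but not explicitly that dates are recorded, so this must be confirmed first.

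The exposed stratum shrinks. Suppose 30% of follow-up is flagged and half of that precedes the distribution. Treating intervals as independent, the variance factor 1/*e* + 1/(1−*e*) rises from 4.76 (*e* = 0.30) to 7.84 (*e* = 0.15), so the standard error grows by √(7.84/4.76) − 1 = 28%. The contrast itself grows from 49% to 100% of its true size, so the change still gains on balance: the flag has about 0.49² × 7.84/4.76 ≈ 0.4 of the information of interval coding. The round terms will take some of that back, by an amount that cannot be computed from the documents.

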## Bayesian Analysis

To complement the primary Frequentist analysis, a Bayesian analysis of the trial will be conducted. Ongoing analyses beyond the primary endpoint, reflecting the perpetual nature of the trial, will be conducted using a Bayesian perspective. The details of the Bayesian analyses will be added to a future update of this SAP.

## Costing and Cost-Effectiveness

Cost-effectiveness analysis will assess the added net costs, added health outcomes (e.g. deaths and DALYs averted), and the ICER (incremental cost-effectiveness ratio): cost per health outcome achieved by going from no intervention to 1 – 11 months, and then to 1 – 59 months as well as comparing the ICERs for census door to door, CHW door to door and CHW fixed point distribution strategies using cost estimates from the Delivery Trials described below. The health outcomes will be mortality (measured in the trial) and DALYs (calculated from mortality). Cost-effectiveness will be assessed from different perspectives: households, community, government health system, and society. Analyses will produce measures of incremental cost-effectiveness: net cost per dose delivered, per death averted, and net cost per DALY averted. The economic analysis will include two-time frames: the study period of 1 – 4 years and a longer time frame highlighting potential long-term effects such as morbidity, mortality and antimicrobial resistance. All results will be subject to sensitivity analyses: one-way (deterministic), two-way, and multi-way (probabilistic) to assess dependence of outcomes on uncertainties in input values.

The cost-effectiveness analysis will incorporate costs and effectiveness as described above. Determination of cost-effectiveness will be according to a Willingness to Pay criterion, e.g. \$150/DALY averted. Costs and DALYs will be discounted at 3% per year. The study will have two time frames: the observed study period (1 – 4 years) and a longer time frame highlighting expected downstream effects and out-of-study effects (see Protocol for further discussion).

Strategies that are more costly but less or equally effective as the next alternative will be considered “dominated”, and removed from consideration, as per best practices. Strategies will be compared by cost from “no intervention” as the base case, going forward by increasing cost. Projected potential benefits in the second time frame may include delayed benefits in the intermediate term based on an observed decay curve, and potentially long-term benefits of the improved health observed during the trial (e.g., nutrition, disease episodes).

To ensure that the model and comparisons are robust, comprehensive sensitivity analyses will be conducted, including one-way, two-way, scenario, threshold and multivariate/stochastic.

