MORDOR I demonstrated that community-level biannual distribution of oral azithromycin to children 1–59 months of age reduced mortality by nearly 14% compared to placebo over 2 years in Malawi, Niger, and Tanzania.⁴ The greatest effect was found in Niger, where communities receiving azithromycin experienced an 18% reduction in mortality compared to those receiving placebo.⁴ Subgroup analyses suggested that the youngest children might benefit the most, with reductions of approximately 23% in children 1–11 months old.⁴ In Niger, azithromycin distributions were associated with an increase in antimicrobial resistance (AMR) to macrolides after 2 years,⁵ though azithromycin remained similarly effective in reducing mortality after 3 years in MORDOR II.⁶

The World Health Organization (WHO) released conditional guidelines for this intervention which include targeting azithromycin distributions to children 1–11 months of age in high mortality settings.⁷ The rationale for targeting this age group is that the youngest children experience the highest risk of mortality and limiting distributions to the youngest children could minimize selection for antimicrobial resistance. However, distributing azithromycin to children 1–11 months alone remains untested, since MORDOR I treated children 1–59 months of age. A crude examination of relative mortality reductions by age group suggests a stronger effect in the younger age groups, but MORDOR was unable to demonstrate a differential effect by age group statistically ($P = 0.20$ for test of interaction of treatment and age).⁴ Moreover, a herd effect could have contributed to the apparent larger effect sizes in the younger groups; treating children 12–59 months may protect children 1–11 months by reducing their exposure to infectious diseases causing mortality. Finally, beyond a possible differential effect by age group, in MORDOR I–Niger there were 5 times as many children aged 12–59 months as children 1–11 months, resulting in nearly twice as many deaths averted in the older age group.⁸ The greatest societal gains may thus come from intervening on a population with a broader risk spectrum instead of targeting only the highest risk subgroups.⁹ More evidence is needed to determine the difference and magnitude of the benefit of targeting different age groups, and of the risk of inducing AMR when distributing to different age groups.

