## Additional Secondary Outcomes

- Mortality rate over 2.5 years by subgroups:
  - Region (Dosso, Tahoua, Maradi, Zinder, and Tillabéri)
  - Child age (1-11m, 12-24m, 24-59m)
  - Child sex
  - Community distance to the nearest Centre de Santé Intégré (CSI)
  - Number of previous community distributions
  - Timing of distribution/seasonality
  - Other interventions
    - Participation in MORDOR trials
    - Participation in and coverage of Seasonal Malaria Chemoprevention (SMC)
    - Participation in trachoma distributions of azithromycin
  - Nutritional status as defined by weight, MUAC, height interval
- Program costs as captured by routine administrative data collection during the study period and by micro-costing activities (T&M)
  - *Measured cost per dose* of azithromycin MDA in Niger for the two age groups (1 – 11 months of age and 1 – 59 months of age)
  - *Variation in measured cost per dose* of azithromycin MDA as a function of community characteristics.
  - *Modeled cost per dose* of an azithromycin MDA in new but similar settings. Values will be assigned to each *input cost category* (personnel, consumables, equipment, services, training, space), *activity* (eg, publicity, transport), and level (communities / household / child) using a fixed and variable cost perspective adjusted to the level, and adjusted for community-level characteristics.
  - Total observed azithromycin MDA program costs, by age group (1 – 11 month versus 1 – 59 month)
- Cost-effectiveness measured by estimated program costs and using measured mortality and estimated DALYs as the effectiveness outcome, compared across arms.
  - ICER for administering azithromycin to the different age groups, comparing the cost and effectiveness of 1 – 59 month vs. 1-11 month.

- Estimated 10 year national-scale effects (health and cost) of scaling up each strategy.
- Other implementation outcomes defined in the Proctor Outcomes Framework,[8] including feasibility and acceptability, as captured during routine administrative and monitoring data collection during the study period and by stakeholder interviews at the participant, community, and health system levels at 2.5 years (Table 3).
- Change in nutritional status over time as defined by weight, mid-upper arm circumference (MUAC), and height interval
- All-cause clinic visits among children 1-59 months of age in the study area during the study period as assessed through passive surveillance of Centre de Santé Intégré records.

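### The cost-effectiveness rule has no extended-dominance step, so the 1–59 month ICER would be too low if the 1–11 month strategy proves extendedly dominated

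*SAP*

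**What the plan says.** SAP 3.5.4, Costing and Cost-Effectiveness, plans a stepwise ICER: "cost per health outcome achieved by going from no intervention to 1 – 11 months, and then to 1 – 59 months". Strategies are ordered from no intervention "as the base case, going forward by increasing cost".

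One removal rule follows: "Strategies that are more costly but less or equally effective as the next alternative will be considered" dominated. This is simple dominance (costlier and no more effective). Such strategies are dropped, with a general appeal to best practice.

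The decision rule is "Determination of cost-effectiveness will be according to a Willingness to Pay criterion", with $150 per DALY averted as an example. SAP 3.5.1, Additional Secondary Outcomes, fixes the comparator for the age-group ICER: "comparing the cost and effectiveness of 1 – 59 month vs. 1-11 month".

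Protocol 4.5.8.2 refers the ICER details to the SAP. Neither document mentions extended dominance, an efficiency frontier or net monetary benefit.

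**The concern.** A sequential ICER against a threshold is a valid guide only if every strategy left in the sequence lies on the efficiency frontier. Simple dominance is the first of two checks. The second removes a strategy whose ICER exceeds that of the next more effective one.

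The second check matters here because of how the strategies are built. If 1–11 is the cheaper programme, 1–59 cannot simply dominate it, whatever the results. The rule would remove 1–11 only if it were no more effective than no intervention. A 1–11 strategy that works but is inefficient therefore stays in the sequence and serves as the comparator for 1–59.

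At stake is the economic side of the choice between the two age ranges. Measured against an inefficient step, 1–59 can appear to pass a threshold that it fails against no intervention.

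**Working it through.** The documents state no cost, ICER or frontier, so there is no economic figure to reproduce.

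**Inputs**

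- Protocol 2, Background and Rationale, on the earlier trial in Niger: "5 times as many children aged 12–59 months as children 1–11 months", "resulting in nearly twice as many deaths averted in the older age group". So the ratio r of deaths averted at 12–59 to those at 1–11 months is about 2.
- SAP 3.2.3 planning effects: 8.8 per 1,000 person-years at 1–11 months and 2.7 at 12–59 months. With 1,116 communities per arm and the stated SDs (0.074 and 0.022), these give 80.2% and 82.6% power. The SAP says about 80%; the second is slightly above, with rounded inputs.
- With five older children per infant, r = 5 × 2.7 / 8.8 = 1.53. Using the stated percentages instead, r = 5 × (0.11 × 24) / (0.19 × 45) = 1.54.

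Two assumptions enter: infants benefit equally under both strategies, and the deaths ratio stands in for the DALY ratio.

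**Condition**

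Let C1, E1 (1–11) and C2, E2 (1–59) be cost and effect relative to no intervention, with E2 = (1 + r)E1. Extended dominance of 1–11 means

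C1/E1 > (C2 − C1)/(E2 − E1), which reduces to C2/C1 < 1 + r.

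- r = 2: C2/C1 below 3.0.
- r = 1.53: C2/C1 below 2.53.

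With about 6 times the doses, this means a cost per dose for 1–59 below 3.0/6 = 50% or 2.53/6 = 42% of that for 1–11.

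**Direction and size**

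C2/E2 is a weighted mean of C1/E1 and (C2 − C1)/(E2 − E1). When 1–11 is extendedly dominated, (C2 − C1)/(E2 − E1) < C2/E2 < C1/E1, so the planned 1–59 ICER is always the lower of the two. With c = C2/C1, the understatement is 1 − (c − 1)(1 + r)/(cr).

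| c (assumed) | r = 2 | r = 1.53 |
|---|---|---|
| 1.5 | 50% | 45% |
| 2.0 | 25% | 17% |
| 2.5 | 10% | 1% |
| 3.0 | 0% | not extendedly dominated |
| above 3.0 | not extendedly dominated | not extendedly dominated |

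**Is the condition plausible?**

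Assume a fixed cost F plus an equal cost v per dose, with one infant to five older children: C1 = F + v, C2 = F + 6v. Then C2/C1 < 1 + r when F/v > (5 − r)/r.

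- r = 2: F/v > 1.5, a fixed share of the 1–59 cost above 1.5/7.5 = 20%.
- r = 1.53: F/v > 2.26, a share above 2.26/8.26 = 27%.
- r = 2, with an older child's dose costing twice an infant's: C2 = F + 11v, F/v > 4, a share above 4/15 = 27%.

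**Hypothetical threshold example**

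Take C1 = $20,000 for 100 DALYs averted and C2 = $48,000 for 300 (c = 2.4, r = 2).

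- 1–11 against none: 20,000/100 = $200.
- 1–59 against 1–11: 28,000/200 = $140.
- 1–59 against none: 48,000/300 = $160.

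At $150 per DALY the planned figure passes and the frontier figure fails. If both costs are scaled together, this occurs only for factors between 150/160 = 0.94 and 150/140 = 1.07, that is, C1 between $18,750 and about $21,430. Outside that range both figures fall on the same side.

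**The case against.** The strongest reply is that the harm is conditional. The documents give no costs, and if C2/C1 exceeds 1 + r, 1–11 belongs on the frontier and the planned sequence is right. The fixed-cost shares depend on an assumed cost model, and the SAP planning effects are detectable effects, not expected ones. All of that stands, and it limits the point to a missing rule.

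The 1–59 against 1–11 contrast is also legitimate in itself. The Protocol's Background notes that WHO guidance includes targeting 1–11 months, and a programme already doing so would want the cost of extending it. That stands too: the contrast misleads only when used alone to choose among all three options.

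The problem would also be visible. Both sequential ICERs are to be reported, and a falling sequence ($200, then $140 above) reveals extended dominance to an informed reader. No data are lost. But the SAP does not say what the analyst must then do. Its appeal to best practice qualifies the simple rule just stated, and the listed sensitivity analyses are there to test uncertain inputs; none is said to change the comparator.

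A reader might infer that 1–11 can never be removed under the rule. The documents do not support this: no intervention is the base case, 1–11 costs more than it, and its efficacy is what the second primary mortality outcome tests.

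**Conclusion.** The gap is real and the direction of error is certain when it occurs: as written, the plan gives too low a 1–59 ICER whenever 1–11 is extendedly dominated. That happens at cost ratios below about 3.0 (Protocol figures) or 2.5 (SAP planning effects). Such ratios are plausible, since door-to-door work has costs shared across ages and Protocol 4.5.8.2 plans to separate fixed from variable costs, but the documents do not establish them.

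A reader might go further and infer that the 1–59 ICER will be wrong, or that the $150 decision will be reversed. Neither follows. The first needs cost data that are not given. The second also needs a threshold lying between the two 1–59 ICERs, and $150 is only an example.

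The limits rest on the two assumptions in the working. If treating older children also protects infants, which the Protocol's Background raises as a possibility, the extra benefit of 1–59 is larger and the limit rises.

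This is a secondary economic analysis, and the mortality tests are untouched. The same omission applies to the delivery strategies compared in that SAP section.

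**What to change.** In SAP 3.5.4, Costing and Cost-Effectiveness, add to the removal rule: after simply dominated strategies are removed, any strategy whose ICER exceeds that of the next more effective strategy is removed as extendedly dominated, and ICERs are recomputed among those left. Apply the rule to the delivery strategies as well.

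Keep the prespecified 1–59 against 1–11 ICER in SAP 3.5.1 as a descriptive contrast, and report 1–59 against no intervention beside it. Net monetary benefit and acceptability curves for all three strategies would be useful but are optional.

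The cost is SAP wording and one extra ratio from data already planned. It is best settled before the cost results are known.
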